12.4. Pharmacokinetic Analyses

The PK parameters that will be assessed in the PK Analysis Population include:

- maximum plasma concentration (C_{max})
- time to maximum plasma concentration (T_{max})
- terminal elimination half-life ($t_{1/2}$)
- apparent clearance (CL/F)
- apparent volume of distribution (V_z/F)
- area under the plasma concentration-time curve from time 0 to time of last quantifiable sample (AUC_{0-t})
- area under the plasma concentration-time curve from time 0 extrapolated to infinity ($AUC_{0-\infty}$)

CD388 concentration in the upper respiratory tract as determined from nasopharyngeal (NP) swabs collection will be summarized and reported separately.

Pharmacokinetic parameter estimation will be performed by non-compartmental analysis (NCA) with Phoenix® WinNonlin® version 8 or higher. The actual elapsed sampling times relative to dosing will be recorded during the study and will be used in the NCA analysis. Pharmacokinetic data handling and analysis will be further detailed in the SAP.

Descriptive statistics will be calculated for plasma concentrations at each individual time point and for all PK parameters. Mean and individual plasma concentration-time profiles will be presented graphically.

Pharmacokinetic samples for CD388 from this study may also be included in a population PK analysis, which will be reported separately.

12.5. Analyses of Metabolite Identification, Pharmacogenomics, Exploratory Biomarkers, and Anti-Drug Antibodies

Analysis of the ADA results is to be determined and may include determination of the subject's positive/negative ADA status at baseline, treatment-emergent ADA in subjects with a negative baseline, as well as a post-baseline increase in titer for subjects with positive ADA at baseline.

Metabolite identification and profiling, CD388 in urine and nasal wash, CD388 DAR distribution, CD388 glycoforms, pharmacogenomics, and exploratory biomarkers will be reported separately.

12.6. Interim Analysis

Three blinded interim analyses of selected safety and PK data, one for the first dose level, another for the second dose level, and a third at the time when the 900 mg cohort completes Day 30. These interim analyses are for internal decision making or health authority interaction. Study team members involved in day-to-day trial related activities will not have access to interim analysis data which might unblind them at the subject level. Unblinding at treatment/group level is permitted as needed to enable the analysis.

12.7. Determination of Study Sample Size

Up to 77 subjects will be enrolled in this study, with approximately 56 of these subjects expected to receive CD388 Injection. The number of subjects was selected to allow sufficient evaluation of safety and tolerability, and PK, and is consistent with standards of practice for first-in-human (FIH) studies.

12.8. Handling of Dropouts and Missing, Unused, and Spurious Data

Every effort will be made to collect all data at specified times. Handling of missing data will be detailed in the SAP.

12.9. Subject Disposition

Enrollment and discontinuations from the study will be summarized, including the reasons for discontinuation.

12.10. Deviation Reporting

Protocol deviations will be summarized. Protocol deviations are defined as any variation from the protocol, including enrollment of a subject who did not meet all inclusion and exclusion criteria and failure to perform the assessments and procedures within the required time frame.

13. INVESTIGATOR REQUIREMENTS

13.1. Protocol Adherence

The Investigator must adhere to the protocol as detailed in this document and agree that the Sponsor must approve any change to the protocol before seeking approval from the IRB/IEC. The Investigator will be responsible for enrolling only those subjects who have met the study selection criteria.

13.2. Electronic Case Report Forms

The contract research organization will make the eCRF accessible to authorized personnel over the internet from an electronic data capture (EDC) system used for the recording of study data as specified by this protocol. All eCRFs must be completed by trained study personnel. The Investigator is responsible for ensuring that the eCRF data are entered and completed in a timely manner.

Once all data queries and issues have been resolved for each subject, the Investigator will electronically sign each subject's eCRF to attest to the accuracy of the data.

13.3. Source Document Maintenance

Source documents are defined as documentation related to original observations and activities of a clinical investigation. Source documents may include, but are not limited to, study progress notes, study- or subject-specific e-mail correspondence, computer printouts, laboratory data, and recorded data from automated instruments. All source documents produced in this study will be maintained by the Investigator and made available for inspections by the Sponsor and by regulatory authorities. The original signed informed consent form (ICF) for each participating subject shall be filed with records kept by the Investigator, and a copy shall be given to the subject.

13.4. Study Monitoring Requirements

An authorized Sponsor representative will conduct site visits to inspect study data, subjects' medical records, and eCRFs in accordance with ICH guidelines, GCPs, and the foreign regulations and guidelines, as applicable. A monitor will be utilized for monitoring ongoing drug accountability and adherence to protocol procedures.

The Investigator will allow representatives of the Sponsor and regulatory authorities to inspect facilities and records relevant to this study.

13.5. Study Completion

The Sponsor requires the following data and materials before a study can be considered complete or terminated:

- Laboratory findings, clinical data, and all special test results from screening throughout the study
- eCRFs (including data queries) properly completed by appropriate study personnel, signed and dated by the Investigator

- Copies of complete drug accountability records (drug inventory log and an inventory of returned or destroyed clinical material)
- Copies of protocol amendments and IRB/IEC approval and notification, if appropriate
- A summary of the study prepared by the Investigator (an IRB/IEC summary letter is acceptable)

End of Study Conduct, for the purpose of clinical trial registries, end of trial notifications to regulatory authorities and IRBs/ECs, will be the latest date on which the last visit in time of any study subject occurs.

14. QUALITY CONTROL AND QUALITY ASSURANCE

Written Standard Operating Procedures (SOPs) will be followed to ensure that the study is conducted, and data are generated, documented (recorded), and reported in compliance with the protocol, GCP, and the applicable regulatory requirements. Quality control will be applied to each stage of data handling. Regular monitoring, as defined in ICH GCP E6(R2), Section 1.38, “The act of overseeing the progress of a clinical trial, and of ensuring that it is conducted, recorded, and reported in accordance with the protocol, SOPs, GCP, and the applicable regulatory requirement(s)”, will be conducted throughout the conduct of the study.

As defined in ICH GCP E6(R2), Section 5.18.1, the purpose of monitoring is to verify that:

- Rights and well-being of the human subjects are protected.
- The reported study data are accurate, complete, and verifiable from source documents.
- The conduct of the study is in compliance with the currently approved protocol/amendment(s), with GCP, and with the applicable regulatory requirements.
- Monitoring is an integral role in the quality control of a clinical trial and is designed to verify the quality of the study.

To fulfill the Quality Assurance requirements of GCP, audits will be conducted to assess and assure the reliability and integrity of a study’s quality control systems and recognized standards.

As defined in ICH GCP E6(R2), Section 5.19, the purposes of an audit are to:

- Ensure subject safety
- Assure compliance to study protocol procedures, regulatory requirements, and SOPs
- Assure data quality

15. PROTECTION OF HUMAN SUBJECTS

This study will be conducted in compliance with the ICH Technical Requirements for Registration of Pharmaceuticals for Human Use E6(R2) Guideline for Good Clinical Practice, the ethical principles of the Declaration of Helsinki, FDA GCP guidelines, and any additional national or IRB/IEC-required procedures.

15.1. Informed Consent

This study will be conducted in compliance with ICH E6(R2) Guideline for Good Clinical Practice pertaining to informed consent. Subjects will give written consent to participate in the study at the first visit, prior to initiation of any study-related procedures, after having been informed about the nature and purpose of the study, participation and termination conditions, risks, and benefits. If a subject is unable to provide written informed consent, the subject's legally acceptable representative (i.e., acceptable to ICH and local law, as applicable) may provide written consent, as approved according to institution-specific guidelines. The ICF must be signed and dated by the subject, or the subject's legally acceptable representative, prior to study participation. A copy of the ICF must be provided to the subject or the subject's legally acceptable representative. If applicable, it will be provided in certified translation for non-English-speaking subjects. Signed ICFs must remain in the subject's study file and be available for verification by Sponsor at any time.

15.2. IRB/IEC Approval

This protocol, the ICF, and all relevant supporting data must be submitted to the IRB/IEC for approval. The protocol, ICF, and any advertisement used to recruit study subjects must be approved by the IRB/IEC. Approval by the IRB/IEC of the protocol and ICF must be obtained before the study may be initiated.

The Investigator is responsible for informing the IRB/IEC of any changes made to the protocol, and to advise them, at least once a year, about the progress of the study. The Investigator is also responsible for notifying the IRB/IEC of any significant AEs that occur during the study.

16. DATA HANDLING AND RECORD KEEPING

Training sessions, regular monitoring of Investigators by Sponsor-designated personnel, instruction manuals, data verification, crosschecking, and data audits will be performed to ensure quality of all study data. Investigator meetings may be performed to prepare Investigators and other study personnel for appropriate collection of study data.

The Sponsor will review and validate study data as defined in the monitoring plan.

It will be the responsibility of the Investigator to ensure that the essential documents are available at the study site. Any or all these documents may be subject to, and should be available for, monitoring by the Sponsor or inspection by the regulatory authorities as defined in the monitoring plan.

16.1. Direct Access to Source Data/Documentation

The Investigator agrees by his/her participation that the results of this study may be used for submission to national or international registration. If required, these authorities will be provided with the name of the Investigator and his or her address, qualifications, and extent of involvement. It is understood that the Investigator is required to provide Sponsor with all study data, complete reports, and access to all study records.

Data generated by this study must be available for inspection by any regulatory authorities, by the Sponsor and by the IRB/IEC as appropriate. At a subject's request, medical information may be given to his or her personal physician or other appropriate medical personnel responsible for his or her welfare. Medical information obtained from subjects during the course of this study is confidential and disclosure to third parties other than those noted above is prohibited.

16.2. Study Drug Accountability

All supplies of CD388 Injection/placebo required for completion of this study will be provided by the Sponsor. It is the responsibility of the unblinded Pharmacy or study staff to ensure that a current record of drug inventory and drug accountability is maintained. Inventory and accountability records must be readily available for inspection by the monitor and are open to inspection at any time by applicable regulatory authorities.

16.3. Retention of Records

Essential documents should be retained until at least 2 years after the last approval of a marketing application in an ICH region and until there are no pending or contemplated marketing applications in an ICH region or at least 2 years have elapsed since the formal discontinuation of clinical development of the investigational product and shipment and delivery of the drug for investigational use is discontinued. These documents should be retained for a longer period, however, if required by the applicable regulatory requirements of specific ICH and non-ICH countries, or by an agreement with the Sponsor. The Sponsor will inform the Investigator/institution as to when these documents no longer need to be retained.

16.4. Long-term Retention of Samples for Additional Future Research

Samples collected in this study may be stored for up to 15 years (or according to local regulations) for additional research. Samples will only be used for research related to influenza virus infection, flu-like disease, and safety, reactogenicity, and immunogenicity of CD388. They may also be used to develop tests/assays related to CD388 and influenza. The research may begin at any time during the study or the post-study storage period.

Stored samples will be coded throughout the sample storage and analysis process and will not be labeled with personal identifiers. Subjects may withdraw their consent for their samples to be stored for research.

17. FINANCING AND INSURANCE

The financing and insurance for this study are outlined in the Clinical Trial Agreement.

18. PUBLICATION POLICY

The data generated in this clinical study are the exclusive property of the Sponsor and are confidential. Authorship on any publication of the results from this study will be based on contributions to study design, enrollment, data analysis, and interpretation of results.

20. APPENDICES

APPENDIX 1. ACCEPTABLE METHODS OF CONTRACEPTION

An acceptable method of contraception includes one of the following:

- Abstinence from heterosexual intercourse
- Hormonal contraceptives (birth control pills, injectable/implant/insertable hormonal birth control products, transdermal patch)
- Intrauterine device (with or without hormones)
- A double barrier method (e.g., condom and spermicide)

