- a. If of childbearing potential – agrees to use a highly effective, preferably user-independent method of contraception (failure rate of <1% per year when used consistently and correctly) for at least 30 days prior to screening and agrees to remain on a highly effective method until 205 days after last dose of study medication. Examples of highly -effective methods of contraception are located in [Appendix 1](#).
- b. If a female of non-childbearing potential – should be surgically sterile (i.e., has undergone complete hysterectomy, bilateral oophorectomy, or tubal ligation/occlusion) or in a menopausal state (at least 1 year without menses), as confirmed by follicle-stimulating hormone (FSH) levels (≥ 40 mIU/mL).
- 4. A woman of childbearing potential must have a negative highly sensitive serum pregnancy test (β -human chorionic gonadotropin) at screening and a negative urine pregnancy test on Day -1 before the first dose of study drug.
- 5. A male subject that engages in sexual activity that has the risk of pregnancy must agree to use a double barrier method (e.g., condom and spermicide) and agree to not donate sperm during the study and until at least 205 days after the last dose of the study medication.
- 6. Good health and without signs or symptoms of current illness.
- 7. Normal clinical examination, including:
 - a. No physical examination findings that an Investigator determines would interfere with interpretation of study results.
 - b. Screening ECG without clinically significant abnormalities (see [Appendix 2](#)).
 - c. Creatinine clearance (CrCL) ≥ 80 mL/min as calculated using the Cockcroft-Gault equation:
$$CrCL = \frac{(140 - age) \times (weight \text{ in kg})}{72 \times (serum \text{ creatinine in mg/dL})} \times (0.85 \text{ if female})$$
- d. Negative urine screen for drugs of abuse and alcohol at screening and Day -1.

- 8. Body mass index (BMI; weight in kg divided by height in m squared) between 18.0 and 32.0 kg/m², inclusive.
- 9. Willing to refrain from strenuous physical activity that could cause muscle aches or injury, including contact sports, at any time from screening through 30 days after any dose of study drug.
- 10. Subject has adequate venous access for blood collection.

Exclusion Criteria

Subjects must NOT meet any of the following exclusion criteria:

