7. SELECTION, DISCONTINUATION, AND WITHDRAWAL OF SUBJECTS

7.1. Subject Inclusion Criteria

Subjects must meet the following inclusion criteria:

1. Willing and able to provide written informed consent.
2. Males and females 18 to 65 years of age, inclusive.
3. A female subject must meet one of the following criteria:
 - a. If of childbearing potential – agrees to use a highly effective, preferably user-independent method of contraception (failure rate of <1% per year when used consistently and correctly) for at least 30 days prior to screening and agrees to remain on a highly effective method until 205 days after last dose of study medication. Examples of highly-effective methods of contraception are located in [Appendix 1](#).
 - b. If a female of non-childbearing potential – should be surgically sterile (i.e., has undergone complete hysterectomy, bilateral oophorectomy, or tubal ligation/occlusion) or in a menopausal state (at least 1 year without menses), as confirmed by follicle-stimulating hormone (FSH) levels (≥ 40 mIU/mL).
4. A woman of childbearing potential must have a negative highly sensitive serum pregnancy test (β -human chorionic gonadotropin) at screening and a negative urine pregnancy test on Day -1 before the first dose of study drug.
5. A male subject that engages in sexual activity that has the risk of pregnancy must agree to use a double barrier method (e.g., condom and spermicide) and agree to not donate sperm during the study and until at least 205 days after the last dose of the study medication.
6. Good health and without signs or symptoms of current illness.
7. Normal clinical examination, including:
 - a. No physical examination findings that an Investigator determines would interfere with interpretation of study results.
 - b. Screening ECG without clinically significant abnormalities (see [Appendix 2](#)).
 - c. Creatinine clearance (CrCL) ≥ 80 mL/min as calculated using the Cockcroft-Gault equation:
$$CrCL = \frac{(140 - age) \times (weight \text{ in kg})}{72 \times (serum \text{ creatinine in mg/dL})} \times (0.85 \text{ if female})$$
8. Body mass index (BMI; weight in kg divided by height in m squared) between 18.0 and 32.0 kg/m², inclusive.
9. Willing to refrain from strenuous physical activity that could cause muscle aches or injury, including contact sports, at any time from screening through 30 days after any dose of study drug.

10. Subject has adequate venous access for blood collection.

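### Inclusion 3a demands highly effective contraception (<1% failure per year) and points to Appendix 1 for examples, but Appendix 1 lists merely acceptable methods with no limit, including double barrier on its own

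*Protocol*

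**What the plan says.** Criterion 3a appears in the Protocol synopsis and in Section 7.1 with the same content. A woman of childbearing potential "agrees to use a highly effective, preferably user-independent method of contraception", with a "failure rate of <1% per year when used consistently and correctly". Use must begin at least 30 days before screening, and she "agrees to remain on a highly effective method until 205 days after last dose of study medication". The criterion then refers the site to Appendix 1: "Examples of highly-effective methods of contraception are located in" that appendix. The synopsis makes the same reference ("Examples of highly -effective methods of contraception are located in").

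The title of Appendix 1 calls its methods acceptable. Its opening line is "An acceptable method of contraception includes one of the following". Four entries follow: abstinence, hormonal contraceptives, an intrauterine device, and "A double barrier method (e.g., condom and spermicide").

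Criterion 5 in Section 7.1 applies to men. A man whose sexual activity carries a risk of pregnancy "must agree to use a double barrier method (e.g., condom and spermicide"). That criterion has no failure-rate limit and does not use the term highly effective.

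**The concern.** An investigator deciding whether a woman's method satisfies 3a will go to the list that 3a names, which is the only list of methods the protocol provides. That list does not repeat the standard it is cited to illustrate. It uses a weaker label and one of its entries matches the separate male standard. A site could follow it in good faith and accept a method without checking it against <1% per year.

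Section 11.8 states that the risks of CD388 in pregnancy are unknown, and this is a first-in-human study. Much of the protocol's other pregnancy provision detects or manages a pregnancy. Criterion 3a is the main provision meant to prevent one, so the list used to apply it should carry its standard.

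**Working it through.** No figure in the plan can be reproduced here; the only number is the <1% threshold, which is an eligibility standard. The check is a comparison of texts, followed by a count of the decisions still open.

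**1. The three places side by side**

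| | Criterion 3a (women) | Appendix 1 | Criterion 5 (men) |
|---|---|---|---|
| Label | highly effective | acceptable | none |
| Failure-rate limit | <1% per year | none | none |
| Rule | one method meeting the limit | any one entry | double barrier |
| Double barrier | not named | listed as sufficient alone | required, same example |
| Duration | to 205 days after last dose | not stated | to at least 205 days after last dose |

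The limit is in 3a and missing from the list that 3a cites. The double barrier entry in Appendix 1 has the same wording and example as criterion 5, and no second method is required with it.

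**2. Do the documents show that double barrier falls below the limit?** No. Neither document gives a failure rate for any of the four entries. The comparison shows that the list does not carry the standard. It does not show that any entry fails it.

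**3. Which decisions are still open**

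- Cohorts 1A to 3B: 6 cohorts × (2 sentinel + 9 main) = 66. Section 4.3 reports 66 subjects already dosed at 50, 150 or 450 mg, which matches.
- Planned total (Section 6.3): 77, and 77 − 66 = 11.
- Cohort 4B: 2 + 9 = 11, of whom 1 + 7 = 8 receive CD388 and 1 + 2 = 3 placebo.

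Planned entry decisions still open are therefore at most 11 subjects of both sexes. In Cohorts 2A to 3B, eligibility is reconfirmed before the second dose (Table 2, footnote c), and a subject who no longer meets the criteria is not redosed (Section 7.4.1). The number of reconfirmations outstanding is not given. Because 3a requires a woman to remain on a highly effective method, the list could also guide a change of method during follow-up.

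**4. Existing safeguards**

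- Contraception from at least 30 days before screening (3a).
- Inpatient stay from Day −1 to Day 30 (Section 6.1). For Cohort 4B the requirement runs to Day 206, so 206 − 30 = 176 days of it fall after discharge.
- Negative serum test at screening and negative urine test on Day −1 (criterion 4).
- Post-dose tests: outpatient visits in Table 1; Days 30, 45, 84, 126, 168 and 206 in Table 3.
- Urine test at Day −1 check-in before dose 2 (Table 2, footnote g). Table 2 schedules none after that.
- Pregnant or nursing women excluded (exclusion 9).
- No second dose if pregnant (Section 7.4.1).
- Immediate notification of the Investigator, report to the Sponsor within 24 hours, counselling, and follow-up to postnatal day 28 or until the pregnancy ends (Section 11.8).

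The first item prevents pregnancy, and the inpatient stay plausibly limits conception while it lasts, although the protocol does not give that as its purpose. The remaining items screen for, detect or manage pregnancy.

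**The case against.** The strongest reply is that 3a already states the limit where it binds. Appendix 1 is cited only for examples, and an appendix of examples need not repeat the criterion. Section 13.1 makes the Investigator responsible for enrolling only subjects who meet the selection criteria, so a site must satisfy 3a whatever the appendix says. The first part stands: the <1% limit formally governs. It does not cure the inconsistency, because 3a itself presents the appendix entries as examples of highly effective methods. A site is in effect told that double barrier qualifies, and nothing in the list prompts a check.

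The second reply is that nothing in the documents shows any listed method to be below standard, so demanding removal of double barrier would assume what has not been shown. This stands, and it limits the remedy. A reader might infer that the protocol knowingly admits women on inadequate contraception, or that double barrier fails <1%. The documents support neither, since they give no failure rates.

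The third reply is that the safeguards are substantial and few subjects are affected. Both parts are fair and keep the point minor. The safeguards do not make the list agree with the criterion, and after dose 2 no pregnancy test is scheduled.

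**Conclusion.** The inconsistency is real and minor. The list cited to apply criterion 3a does not carry its <1% limit, and it includes, as sufficient alone, the method that the protocol sets for men under a different standard. The texts show this without any outside figure.

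No pregnancy risk and no count of affected women can be stated: the documents give no failure rates, no number of women of childbearing potential and no method use. A reader might take the 11 remaining entries as 11 women at risk. That figure is only a ceiling on planned Cohort 4B entries of both sexes, 3 of them on placebo, and it assumes that the 66 subjects in Section 4.3 are the full planned Cohorts 1A to 3B. Endpoints, sample size and analysis are unaffected. The edit is still worth making because the list guides eligibility decisions in a first-in-human study.

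**What to change.** Amend Appendix 1 as follows:

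- Retitle it as highly effective methods for criterion 3a (women of childbearing potential).
- State that a listed method qualifies only if it meets the <1% per year limit in 3a.
- Move double barrier to criterion 5 (men), or mark it as an adjunct to another listed method for women, unless the sponsor documents that it meets <1% per year.

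Do not resolve the mismatch by loosening 3a. The synopsis and Section 7.1 cite the same appendix, so one edit corrects both.

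The cost is one appendix change in an amendment and possibly slightly fewer eligible women. Abstinence, hormonal methods and intrauterine devices stay on the list, subject to the limit, and Section 8.5 already exempts hormonal contraceptives from the medication restriction.
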